2.3.3 Medical History

Any significant prior or active medical condition at the time of signing informed consent will be coded using MedDRA. These medical conditions will be summarized by primary system organ class and preferred term will be presented for the randomized set. Psoriatic arthritis history and psoriasis history will be summarized separately by pre-specified categories recorded on the eCRF.

To establish a baseline level of cardiovascular risk, the number and percentage of patients with pre-solicited cardiovascular risk factors will be summarized by treatment group will be presented for the randomized set. The number of cardiovascular risk factors that each patient has will also be summarized by treatment group. If it is unknown whether or not a patient currently or previously experienced a specific cardiovascular risk factor, it will be assumed that cardiovascular risk factor did not occur for that patient.

2.4 Treatments (study treatment, concomitant therapies, compliance)

2.4.1 Study treatment / compliance

The analysis of study treatment data will be based on the safety set.

The number of active and placebo injections will be summarized by treatment group and treatment period.

In case it cannot be identified from the data collected or assumed from the planned treatment whether an injection contained placebo or secukinumab, as if this occurs for subjects in the 300 mg treatment groups or in the placebo treatment group, respectively,

when subjects should receive two identical injections, it will be assumed that they received secukinumab or placebo, respectively, as planned.

The duration of exposure to study treatment will be summarized by the actual treatment received or treatment sequence for each treatment period. In addition, the number of subjects with cumulative exposure of at least certain time thresholds will be displayed. The following categories will be presented: “any exposure”, “<1 week”, “≥1 week” “≥2 weeks”, “≥3 weeks”, “≥4 weeks”, “≥8 weeks”, “≥12 weeks”, and so on with an increase of time threshold by 4 weeks until there are no subjects in the category or the last category is presented.

For treatment period 1, the end date for the calculation of duration of exposure will be the earlier of:

- a. Date of last injection in treatment period 1 + 84 days, and
- b. Date of first injection in treatment period 2

For treatment period 2, the end date for the calculation of duration of exposure will be the earlier of:

- a. Date of last injection in treatment period 2 + 84 days, and
- b. Date of first injection in treatment period 3

For treatment period 3 (extension period), the end date for the calculation of duration of exposure will be the date of last injection in treatment period 3 + 84 days.

For patients with death as an event, end date for calculation of duration of exposure will be the date of death if it is earlier than the date of last injection + 84 days.

Duration of exposure (years) = duration of exposure (days) / 365.25

The analyses of duration of exposure described above will be done for the double-blind placebo controlled period (Period 1), Treatment Period 2 – open-label treatment period (Week 12 to Week 24) and Treatment Period 3 – extension period (Week 24 to Week 52).

Compliance

Compliance will be calculated based on documented study drug administrations and displayed by treatment group. It is calculated as follows:

Compliance (%) = $100 * (\text{total no. of injections administered}) / (\text{no. of injections prescribed})$

. Treatment compliance for subjects will be summarized for subjects for each treatment period of the study.

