The date of last dose will be collected via the eCRF. The subject's exposure will be calculated considering the end of treatment period visit (e.g., treatment period 3 completion visit). If a subject discontinued early, then the last visit during the treatment period is considered (e.g. last visit in treatment period 2, if subject discontinued from treatment period 2).

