Algorithms for date imputations will be provided in Appendix 5.1.2.

Exposure time-adjusted incidence rates including 95% CIs will be presented for the entire treatment period. A graphical display of the crude rates and exposure-adjusted incidence rates will be presented for all AEs and SAEs by SOC.

In addition, for the legal requirements of clinicaltrials.gov and EudraCT, 2 required tables on TEAEs which are not SAEs with an incidence greater than 2% and on treatment emergent AEs and SAEs suspected to be related to study treatment will be provided by primary SOC and PT on Safety set population.

If for the same patient, several consecutive AEs (irrespective of study treatment causality, seriousness and severity) occurred with the same primary SOC and PT:

- A single occurrence will be counted if there is ≤ 1 day gap between the end date of the preceding AE and the start date of the consecutive AE
- More than one occurrence will be counted if there is > 1 day gap between the end date of the preceding AE and the start date of the consecutive AE

For occurrence, the presence of at least one SAE/SAE suspected to be related to study treatment/non-SAE has to be checked in a block e.g., among AEs in a ≤ 1 day gap block, if at least one SAE is occurring, then one occurrence is calculated for that SAE.

The number of deaths resulting from SAEs suspected to be related to study treatment and SAEs irrespective of study treatment relationship will be provided by SOC and PT.

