2.15 Interim analysis

Prior to the Week 52 database lock and end of study reporting there are 3 other analyses planned: a blinded sample size re-estimation (SSR), a Week 12 and a Week 24 analysis.

Blinded Sample Size Re-estimation (SSR)

The blinded SSR will be performed when the first 60 patients have completed the Week 12 visit. The pooled standard deviation of the change from baseline in GLOESS at Week 12 will be calculated for the 60 patients and the pooled change will be transformed based on the placebo response observed in the FUTURE 2 study (CAIN457F2312), roughly 50% of secukinumab. These estimates will be used to decide whether the study should continue as planned.

Although the study is originally designed to have at least 90% power, any change in sample size will be based on 80% power due to enrolment feasibility.

Week 12 analysis

The analysis of the primary and secondary efficacy variables will be performed after all patients complete the Week 12 visit. This analysis will also include exploratory variables outlined up to Week 12 and all available safety data.

Week 24 analysis

The analysis of the exploratory variables up to Week 24 will be performed after all patients complete the Week 24 visit. This analysis will also include all available safety data.

3 Sample size calculation

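### The exposure rule in SAP 2.4.1 has no data cut-off limit, so at the Week 12 and Week 24 analyses it counts secukinumab time that lies after the cut-off

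*SAP*

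**What the plan says.** SAP 2.4.1 sets the end of exposure period by period.

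- Period 1: the earlier of two dates, "Date of last injection in treatment period 1 + 84 days, and" and "Date of first injection in treatment period 2".
- Period 2: the same construction, "Date of last injection in treatment period 2 + 84 days, and" set against the first Period 3 injection.
- Period 3: a single date, "the end date for the calculation of duration of exposure will be the date of last injection in treatment period 3 + 84 days".
- Death: the "end date for calculation of duration of exposure will be the date of death if it is earlier than the date of last injection" plus 84 days.

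No limit at last contact or at a data cut-off appears in that section.

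SAP 2.1.1 words exposure differently: "exposure will be calculated considering the end of treatment period visit", or the last visit in the treatment period for a patient who discontinues early.

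SAP 2.15 says of the Week 12 analysis: "This analysis will also include exploratory variables outlined up to Week 12 and all available safety data". The Week 24 analysis likewise takes in all available safety data. SAP 2.9.1 reports adverse events per 100 patient-years and adds: "Exposure time-adjusted incidence rates including 95% CIs will be presented for the entire treatment period". SAP 1.1 states that Week 12 summary results will be shared internally and externally.

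**The concern.** In an incidence rate, events and person-time must cover the same interval. At an interim cut the events stop at the cut-off. For a patient still on treatment, the time under 2.4.1 does not: it runs to 84 days after the most recent injection, which is at most 4 weeks old.

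The extra time falls almost wholly on secukinumab. Placebo time of patients who switch stops at their first open-label injection, and from then on every continuing patient is on secukinumab. The exposure tables would therefore overstate secukinumab patient-years, and any rate built on them would understate secukinumab event rates, in results that may leave the sponsor.

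**Working it through.** **Inputs from the SAP**
- Exposure end dates: 2.4.1, as above.
- Dosing days: 5.4, Table 5-2, giving Days 1, 8, 15, 22, 29, 57, 85, then every 28 days to Day 365.
- 82 patients per arm: 1.1.
- Secukinumab time starts on Day 1 in Group 1 and Day 85 in Group 2 (1.1; 2.9.1 assigns events to the last treatment received).
- Timing of the two analyses: 2.15.

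**Assumptions, not in the SAP**
- Uniform enrolment over R months, no drop-out, all doses on schedule.
- The cut-off is the day the last patient reaches Day 85 (Week 12 analysis) or Day 169 (Week 24 analysis).

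**1. The plan's own schedule.** Last dose Day 365 + 84 = Day 449, which is the scheduled Week 64 day in Table 5-1. For a completer at the final analysis, counted and observed time agree: excess 0.

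**2. Period 1.** For a patient who continues, the end is min(57 + 84, 85) = min(141, 85) = Day 85. All of it is observed, in both arms.

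**3. One patient still being dosed at the cut-off.** Let d be the study day at the cut-off and L the day of the latest injection.
- Counted end = L + 84
- Observed end = min(d, L + 84)
- Excess = max(0, L + 84 − d)

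With 28-day dosing, d − L runs from 0 to 27, so the excess runs from 84 down to 57 days. Examples:
- Period 2 rule: d = 100, L = 85, no Period 3 injection yet. Counted to Day 169, excess 69 days.
- Period 3 rule: d = 300, L = 281. Counted to Day 365, excess 65 days.
- Last patient enrolled, dosed at the Week 12 visit: d = L = 85, excess 84 days.

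**4. All 164 patients.** The periods join end to end, so a patient's total secukinumab time runs from the first secukinumab dose to L + 84. Summing counted and observed time over both arms, with understatement = 1 − observed / counted:

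| Analysis | R (months) | Counted PY | Observed PY | Rate understated by |
|---|---|---|---|---|
| Week 12 | 6 | 91.5 | 59.6 | 34.8% |
| Week 12 | 12 | 129.1 | 100.6 | 22.0% |
| Week 12 | 18 | 146.6 | 127.5 | 13.0% |
| Week 12 | 24 | 155.3 | 141.0 | 9.2% |
| Week 12 | 36 | 163.9 | 154.4 | 5.8% |
| Week 24 | 6 | 129.2 | 97.4 | 24.7% |
| Week 24 | 12 | 155.0 | 133.8 | 13.7% |
| Week 24 | 18 | 164.1 | 149.7 | 8.8% |
| Week 24 | 24 | 168.3 | 157.7 | 6.3% |
| Week 24 | 36 | 172.6 | 165.6 | 4.1% |

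PY = patient-years. Percentages come from unrounded totals, so the last digit can differ by 0.1 from the rounded columns.

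**5. Cross-check.** For Week 12 with R = 12, the mean excess is 63.4 days per patient: 63.4 × 164 / 365.25 = 28.5 PY, and 129.1 − 100.6 = 28.5 PY.

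**The case against.** **The rule may be silent on ongoing patients.** A patient in mid-period has no final injection yet, so one can argue that 2.4.1 leaves the case open and does not prescribe future credit. In part this stands: a careful programmer might truncate unprompted. But the algorithm is explicit to the day and names its exceptions, and the cut-off is not among them. Taken literally, the latest recorded injection is the last one.

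**Section 2.1.1 is visit-based.** A reader might infer that the SAP nowhere limits exposure to observed contact. That goes too far: 2.1.1 would end a discontinued patient's exposure at the last visit in the treatment period. It conflicts with 2.4.1, however, and gives no end date for a patient who has neither completed the period nor discontinued.

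**Interim rates are inferred.** The SAP does not say outright that exposure-adjusted rates are produced at Weeks 12 and 24; that is read from the inclusion of all available safety data. This stands, so the effect on rates is conditional. The effect on exposure summaries needs only that those summaries are run at the two analyses.

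**The randomised comparison.** A reader might conclude that the placebo-controlled safety comparison is tilted towards secukinumab. Step 2 shows that it is not for patients who continue. The exceptions are patients in either arm who stop in Period 1 and whose 84-day tail passes the cut-off.

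**The extreme case.** If everyone enrolled on one day, the Week 12 figure would be 1 − 84/252 = 67% and the Week 24 figure 1 − 252/420 = 40% (days for one patient from each arm). SAP 3.1 rules this out: 72 patients had already reached Week 12 while the target was being reset to 164.

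**Conclusion.** The point holds for the open-label and entire-period denominators at the Week 12 and Week 24 analyses. The Period 2 and Period 3 rules credit each patient still on 4-weekly dosing with about 56 to 84 days that have not been observed. Secukinumab exposure is overstated, and any exposure-adjusted secukinumab rate produced at those analyses is understated.

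The size depends on enrolment duration, which the SAP does not give. Under the stated assumptions, over 36 down to 6 months, the understatement is about 6% to 35% at Week 12 and 4% to 25% at Week 24. A cut-off later than assumed would change these figures.

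At the final analysis, the 84-day tail matches the treatment-emergent window in 2.9.1 and the follow-up visit. Only patients lost before that visit are over-credited there. The efficacy analyses are not touched. Separately, 2.1.1 and 2.4.1 state different exposure rules and must be reconciled whatever is decided about the cut-off.

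**What to change.** In 2.4.1, end exposure in each period at the earliest of: the dates already listed for that period, death, the date of last study contact and, for the Week 12 and Week 24 analyses, the data cut-off date. Reword the exposure sentences in 2.1.1 to point to this rule. It would also help to state in 2.15 whether exposure-adjusted rates are produced at the two earlier analyses.

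The cost is one added sentence in 2.4.1, a short edit in 2.1.1 and one more minimum term in the exposure derivation. Completers' exposure at the final analysis does not change.

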2.4.2 Prior & concomitant medications

Concomitant medications entered into the database will be coded using the World Health Organization Drug Reference List, which employs the Anatomical Therapeutic Chemical (ATC) classification system.

Prior and concomitant medications will be summarized by treatment group in separate tables for the safety set unless otherwise specified. Medications will be presented in alphabetical order, by ATC codes and grouped by *anatomical main group* (the 1st level of the ATC codes). Tables will also show the overall number and percentage of subjects receiving at least one drug of a particular ATC code, at least one drug in a particular anatomical main group and any Methotrexate or any Corticosteroids.

Prior medications are defined as drugs taken and stopped prior to first dose of study treatment. Any medication given at least once between the day of first dose of study treatment and the last day of study visit will be a concomitant medication, including those which were started pre-baseline and continued into the treatment period.

Prior or concomitant medication will be identified based on recorded or imputed start and end dates of medication taken.

Prior & concomitant procedures will be coded using the Medical dictionary for regulatory activities (MedDRA) terminology. Prior and concomitant procedures will be summarized by treatment group for the safety set unless otherwise specified and will be displayed by treatment period.

Prior psoriasis-psoriatic arthritis therapies details will also be listed for each patient and summarized by therapy type (biologic systemic, non-biological systemic therapy {Methotrexate, Corticosteroid, NSAID and DMARDs}, topical, phototherapy and photo chemotherapy).

The number and percentage of subjects receiving prior and concomitant therapies from the *Prior Psoriasis-Psoriatic Arthritis Therapy eCRF* will be presented by randomized treatment group as well as the reasons for stopping their therapies (primary lack of efficacy, secondary lack of efficacy, lack of tolerability, other).

2.5 Analysis of the primary objective

The primary objective is to demonstrate that there is a difference between secukinumab and placebo in terms of joint synovitis response over 12 weeks as measured by the PDUS Global OMERACT-EULAR Synovitis Score (GLOESS) of the affected joints (out of 48 joints) in PsA patients with an inadequate response (IR) to non-biologic DMARDs (reference Appendix 5.7 for further details).

2.5.1 Primary endpoint

The primary analysis variable is the change from baseline in GLOESS over 12 weeks.

The analysis of the primary efficacy variable and all other efficacy variables will be based on the FAS. All efficacy variables will be summarized using descriptive statistics.

2.5.2 Statistical hypothesis, model, and method of analysis

The statistical hypothesis for the GLOESS being tested is that there is no difference in the mean change from baseline scores over 12 weeks in the secukinumab regimen vs the placebo ± MTX (and non-biologic DMARDs) regimen.

Between-treatment differences in the change in GLOESS will be evaluated using a mixed-effect model repeated measures model (MMRM) with treatment regimen, center and analysis visit as factors and weight and baseline GLOESS as continuous covariates. Treatment by analysis visit will be included as an interaction term in the model. An unstructured covariance structure will be assumed for this model. If the model does not converge, the compound symmetry covariance structure will be used. The data will be assumed to be missing at random (MAR).

[figure not shown]

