2.6.2 Statistical hypothesis, model, and method of analysis

The following null hypotheses will be included in the testing strategy and type-I-errors will be set such that a family-wise type-I-error of 5% is kept:

Primary objective:

- H_1 : secukinumab s.c. is not different to placebo regimen with respect to the change in GLOESS from Baseline to Week 12.

[figure not shown]
See section 2.5.2 for details.

Key secondary objectives:

- H_2 : secukinumab is not different to placebo regimen with respect to ACR 20 response at Week 12.
- H_3 : secukinumab s.c. is not different to placebo regimen with respect to ACR 50 response at Week 12.
- H_4 : secukinumab s.c. is not different to placebo regimen with respect to the change in SPARCC enthesitis index from Baseline to Week 12.

No hypotheses other than H_1 to H_4 will be considered. The family wise error will be set to $\alpha=5\%$ (1-sided). The graphical approach of Bretz ([Bretz et al 2009](#)) for sequentially rejective testing procedures is used to illustrate the hierarchical testing strategy ([Figure 1](#)).

Figure 1 Testing strategy

The family-wise error will be set to $\alpha = 5\%$ (1-sided). H_1 is tested at α (1-sided). The following hypotheses will be tested sequentially and are included in the hierarchical testing strategy and type-I-errors will be set such that a family-wise type-I-error of 5% is kept:

The testing sequence will continue to H_2 at α (1-sided) only if H_1 has been rejected.

Similarly, the testing sequence will continue to H_3 at α (1-sided) only if H_2 has been rejected. This process will continue as each hypothesis is rejected up to H_4 .

Of note, in the description above, rejection of a hypothesis refers to rejection of the 1-sided hypothesis; however, the level of a rejected hypothesis is only passed on

(according to the graphical procedure) for the test of another hypothesis if the treatment effect is in favor of secukinumab.

ACR 20 at Week 12

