2.7 Analysis of secondary efficacy objective(s)

2.7.1 Secondary endpoints

The following secondary efficacy variables will be analyzed using the FAS population:

- Change in GLOESS from Baseline to Week 8.
- Change in OMERACT enthesitis score from Baseline to Week 12 for each of the 5 targeted entheses.

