3.1 Determination of sample size

This study was designed using data for abatacept in the APPRAISE study (RA study to assess early response to abatacept + MTX ([D'Agostino et al, 2016](#)), to test the superiority of secukinumab compared to placebo at the 5% significance level using a 2-sided test. Assuming a difference in the mean change from Baseline at Week 12 in OMERACT global PDUS score of -5.8 with a pooled standard deviation of 13.2, 218 patients in total (109 patients per arm) were estimated to achieve a power of 90% ([EAST 6](#)).

A blinded SSR was performed once the first 60 patients completed the Week 12 visit to evaluate the assumptions used in the sample size calculations. The statistical test for the primary endpoint has been changed from a 2-sided to a 1-sided test.

The first 60 patients to reach Week 12 have a pooled mean change from Baseline at Week 12 in OMERACT global PDUS score of -5.25 with a pooled standard deviation of 9.527. Using the estimated placebo effect of roughly 50% of secukinumab based on data from the FUTURE 2 study (CAIN457F2312) as in the original sample size calculation, the pooled PDUS score change of -5.25 translates to an assumed change of -7.000 and -3.500 for the secukinumab and placebo group, respectively, providing a difference of 3.500 between the groups. Adapting the original sample size calculation to be 1-sided with the power relaxed to 80%, 184 patients in total (92 patients per arm) are required ([EAST 6](#)).

At the time of the blinded sample size calculation, 72 patients were available who had reached their Week 12 visit, to provide the most accurate estimation, all data available were considered i.e. the first 72 patients as opposed to the first 60 patients. Using all available data a difference in the mean change from Baseline at Week 12 in OMERACT global PDUSscore of 4.352 was observed with a pooled standard deviation of 9.822. At the 5% significance level using a 1sided test, 126 patients are needed to achieve a power of 80% ([EAST 6](#)).

The 2 calculations produce a sample size range of 127-185 patients; thus, the sample size will be adjusted to a new target of 164 patients in total (82 patients per arm). This is mid-

way point of the range plus a 5% adjustment based on the observed drop-out rate of patients prior to Week 12 observed at the time of this calculation.

For the secondary variables:

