5.5 Statistical models

5.5.1 Primary analysis

The statistical hypothesis for the GLOESS being tested is that there is no difference in the mean change from baseline scores over 12 weeks in the secukinumab regimen vs the placebo regimen.

The model to be tested is as follows:-

Change from baseline in GLOESS = Treatment + center + analysis visit + weight + baseline GLOESS + Treatment * analysis visit.

The procedure PROC MIXED will be used to perform the MMRM analysis. Treatment regimen, center and analysis visit will be set as class variables. The model statement will be based on the formula outlined above. The repeated statement of PROC MIXED will set analysis visit as the repeated variable and the type option will set the convergence method. An unstructured covariance structure will be assumed for this model (type=UN). If the model does not converge, the compound symmetry covariance structure will be used (type=CS). The data will be assumed to be missing at random (MAR). The overall method will be set to REML.

From this analysis, the adjusted changes for each treatment group, the difference between the adjusted changes (secukinumab group vs placebo), 95% confidence interval around the difference and 1-sided p-value will be calculated for each visit.

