5.5.2 Key secondary analysis

The key secondary objectives:

- H_2 : secukinumab is not different to placebo regimen with respect to ACR 20 response at Week 12.
- H_3 : secukinumab s.c. is not different to placebo regimen with respect to ACR 50 response at Week 12.
- H_4 : secukinumab s.c. is not different to placebo regimen with respect to the change in SPARCC enthesitis index from Baseline to Week 12.

H_2 will be tested as follows:-

ACR 20 at Week 12 = Treatment + weight.

The procedure PROC LOGISTIC will be used to perform the logistic regression analysis. Treatment regimen will be set as a class variable. The model statement will be based on the formula outlined above. Reference coding will be used in the model. The odds ratios will be computed for comparison of secukinumab versus placebo using the logistic regression model fitted. If the initial model does not converge Firth's penalized maximum likelihood estimation method will be used.

H_3 will be analysed analogous to H_2 above.

H_4 will be analysed analogous to the primary efficacy variable.

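### Does the wording of the primary analysis leave open which GLOESS contrast tests H1, or which joints enter the score?

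*SAP*

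**What the plan says.** **Time point.** Section 2.5.1 says "The primary analysis variable is the change from baseline in GLOESS over 12 weeks". Sections 2.5.2 and 5.5.1 carry the same time phrase into the null hypothesis: "there is no difference in the mean change from baseline scores over 12 weeks in the secukinumab regimen". The model is an MMRM with a treatment-by-visit interaction, and 5.5.1 states its output: "95% confidence interval around the difference and 1-sided p-value will be calculated for each visit".

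The testing strategy in 2.6.2 gives H1 as "secukinumab s.c. is not different to placebo regimen with respect to the change in GLOESS from Baseline to Week 12" and then refers back to 2.5.2. Section 2.7.1 lists "Change in GLOESS from Baseline to Week 8" as a separate secondary endpoint. Section 2.15 bases the re-estimation on Week 12: "The pooled standard deviation of the change from baseline in GLOESS at Week 12 will be calculated for the 60 patients". So does the design in 3.1: "Assuming a difference in the mean change from Baseline at Week 12 in OMERACT global PDUS score of -5.8". Section 5.5.2 says that H4, a Week 12 change in SPARCC, "will be analysed analogous to the primary efficacy variable".

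**Joints.** Section 2.5 describes GLOESS as the score of the affected joints out of 48 and refers to Appendix 5.7. Appendix 5.7 says the 24 pairs are scanned at each visit, then adds a note that after Baseline only affected joints are assessed. Appendix 5.10 repeats the first statement without the note and defines GLOESS as a plain sum over the joints examined. Section 2.5.3 covers patients with no post-baseline value at all; it does not mention a single unscanned joint.

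**The concern.** H1 must be rejected before H2 to H4 can be tested, so it should be clear which p-value decides it. A model with a treatment main effect and a treatment-by-visit interaction can yield a Week 12 difference or an effect averaged over visits. The sections that define the primary analysis use wording that fits either, and the cross-reference from 2.6.2 leads back to that wording. If the choice stayed open until the data were seen, the one-sided error rate for H1 would exceed 5%.

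The score raises a second doubt. In a plain sum, a joint that is not scanned adds nothing, just like a joint of grade 0, so a missed joint would look like improvement. HAQ-DI has a rule for incomplete categories (5.13). The primary variable has no such rule in the visible text.

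**Working it through.** **1. The plan's own figures.** Per arm, n = 2(z_alpha + z_power)^2 SD^2 / d^2, with inputs from 3.1.
- Original design (d = 5.8, SD 13.2, two-sided 5%, 90% power): 2 x (1.960 + 1.282)^2 x 13.2^2 / 5.8^2 gives 109 per arm, 218 in total, as stated.
- First 60 patients (d = 3.5, SD 9.527, one-sided 5%, 80% power): 2 x (1.645 + 0.842)^2 x 9.527^2 / 3.5^2 gives 92 per arm, 184 in total, as stated.
- First 72 patients (d = 4.352, SD 9.822, one-sided 5%, 80% power): 63 per arm, 126 in total, as stated.
- Target: the midpoint of 127 and 185 is 156, and 156 x 1.05 = 163.8, about 164.

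All of these inputs are Week 12 differences, so the trial was sized for a Week 12 test.

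**2. Power of that test.** Take 156 evaluable patients (164 less 5%). Z = d / (SD x sqrt(4/156)), with sqrt(4/156) = 0.1601.
- 3.5 / (9.527 x 0.1601) = 2.294; power = Phi(2.294 - 1.645) = 74.2%.
- 4.352 / (9.822 x 0.1601) = 2.767; power = Phi(2.767 - 1.645) = 86.9%.

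**3. How far a visit average could disagree.** The SAP gives no correlations and no onset profile, so these are assumptions: equal variances and a common correlation rho of 0.4 to 0.8. For k visits, Z_avg = Z x f / s. Here f is the mean effect across visits as a fraction of the Week 12 effect, and s = sqrt((1 + (k - 1) rho)/k) is also the correlation between the two statistics. Disagreement = P(Week 12) + P(average) - 2 P(both).
- Example, visits at Weeks 4, 8 and 12, linear onset, rho = 0.6, first-60 inputs: f = (4 + 8 + 12)/36 = 0.667; s = sqrt(2.2/3) = 0.856; Z_avg = 2.294 x 0.667 / 0.856 = 1.786. The probabilities are 0.742, 0.556 and 0.538, so disagreement is 0.742 + 0.556 - 2 x 0.538 = 0.22.
- Full range with those three visits, linear to immediate onset: 6% to 25%.
- Visits at Weeks 1, 2, 4, 8 and 12: 7% to 21% if f is at least 0.725, and 36% to 48% with linear onset (f = 27/60 = 0.45).
- If either contrast could be chosen after the fact, simulation with rho 0.5 to 0.85 gives a one-sided error of 6.3% to 7.7%.

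**4. Does the plan allow the average?** H1 is labelled and stated for Week 12. Section 5.5.1 requests a difference, interval and p-value at each visit and no visit average. The Week 12 row of that output is the test of H1, and the Week 8 row is the secondary endpoint in 2.7.1. If the primary endpoint were an average over visits, the Week 12 sizing in 3.1 and the Week 12 re-estimation in 2.15 would have been done on a different quantity.

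**5. Joints.** Suppose 5% to 20% of patients miss one grade-2 joint (assumed). The arm mean shifts by 0.05 x 2 = 0.1 to 0.20 x 2 = 0.4 points. Equal rates in both arms cancel in the expected difference. Only if all the misses fell in one arm would the full shift enter the comparison: 0.1/3.5 to 0.4/3.5 = 3% to 11%, or 0.1/4.352 to 0.4/4.352 = 2% to 9%.

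**The case for a change.** The strongest case for a change is that a confirmatory contrast should be named where the primary analysis is defined, not gathered from other sections. That the phrase appears in 2.5.1, 2.5.2 and 5.5.1 as well as in the objective is a fair criticism of the drafting. It does not show that two analyses are on offer: only one passage states H1 within the testing strategy, and it names Week 12. A figure is also missing from the text at hand at the end of 2.5.2 and again directly after H1, so it is not certain that 2.5.2 is silent.

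On joints, 5.7 and 5.10 do read differently. But 5.7 contains the same every-visit sentence and then qualifies it, the primary objective speaks of affected joints, and 2.5 refers the reader to 5.7. What counts as an affected joint and which joints are rescanned are acquisition rules that a protocol commonly holds, and the protocol is not shown. The silence on a missed joint is real in the visible text. However, 2.5.4 names missing data as a topic and is then partly redacted, so a rule may exist. How an affected but unscanned joint enters the sum is a fair question to put to the sponsor, but not evidence of a defect.

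**Conclusion.** No change to the plan follows. The time phrase is loose wording that the SAP itself resolves: an analyst who reads 5.5.1 together with H1 takes the Week 12 treatment difference from the MMRM. Sample size, model and alpha are the same whether or not the wording is tidied. The disagreement figures of 6% to 25% (up to 48% in the least favourable assumed case) compare the Week 12 test with an analysis that no passage requests, so they do not measure a risk in this plan.

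The missing note in 5.10 is a clerical omission, and 5.7 is the section to which the primary objective points. The missed-joint rule is a detail that analysts can fill sensibly, with an expected shift of 0.1 to 0.4 points in an arm mean under the assumed rates and no expected effect on the comparison if the arms are alike. This view rests on reading the SAP as a whole and on the absence of any passage suggesting that missed scans differ by arm.
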